5.2.1.1.1 Dose Limiting Toxicity Criteria

The same DLT criteria will be utilized for study Part A and Part B. All toxicities will be graded using CTCAE v 4.03. The DLT window of observation will begin at the administration of the initial dose of ADXS31-142 and end 1 week following the second dose of ADXS31-142. The occurrence of any of the following toxicities will be considered a DLT, if judged by the investigator to be possibly, probably or definitely related to study treatment administration. Treatment modifications for DLT are shown in Table 8 and Table 9.

General:

1. Prolonged delay (>2 weeks) in initiating the second dose due to treatment-related toxicity
2. Missing the second dose of ADXS31-142 or pembrolizumab (MK-3475) as a result of AE(s) during the first cycle.

Hematologic:

1. Grade 4 hematologic toxicity.
2. Febrile neutropenia, defined as absolute neutrophil count (ANC) $< 1000/\text{mm}^3$ with a single temperature of >38.3 degrees C (101 degrees F) or a sustained temperature of ≥ 38 degrees C (100.4 degrees F) for more than 1 hour.
3. Grade 3 thrombocytopenia lasting >72 hours.
4. Grade 4 thrombocytopenia.

Non-Hematologic:

1. \geq Grade 3 non-hematologic toxicity, (excluding nausea, vomiting and/or diarrhea lasting <3 days and reversible with medical intervention).
2. Grade 3 non-hematologic laboratory value that does not downgrade to Grade 2 within 3 days after onset of the event despite optimal medical management (excluding transient Grade 3 laboratory value abnormalities reversible within 5 days and without medical intervention).
3. Listeremia: positive blood culture(s) along with persistent (for 72 hours post dose) symptoms consistent with listeremia (e.g., fever and muscle aches, often preceded by diarrhea or other gastrointestinal symptoms).
4. \geq Grade 3 flu-like or cytokine release symptoms that persist for >24 hours after ADXS31-142 administration despite symptomatic treatment (Refer to Section 7.2.3.2).

Subjects who experience a DLT at Dose Level -1 of 0.5×10^9 will be discontinued from study treatment. However, subjects who experience a DLT at DL 1 of 1×10^9 may be eligible to receive ADXS31-142 at a lower dose level for subsequent doses and cycles following discussion and agreement between the Investigator and Sponsor.

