5.2.1.2.2 ADXS31-142

The most likely anticipated AEs associated with ADXS31-142 are comprised primarily of individual flu-like symptoms (e.g., fatigue, lethargy and low grade fever) or cytokine release symptoms (e.g., constitutional symptoms such as fever, chills, rigors, headache, nausea, vomiting, tachycardia, shortness of breath, hypotension, and rash). These symptoms usually present within 2-4 hours after the completion of infusion and are often mild to moderate and transient in nature or respond quickly to symptomatic treatment. In rare instances, they may last up to 24 hours. No cumulative or delayed toxicity has been observed.

Less likely AE's include increase heart rate, low blood pressure, muscle aches, headaches, allergic reaction, changes in blood chemistry, changes in blood counts, and short term changes in liver function.

Rare but serious AEs include high fever, difficulty breathing and hypotension.

██████████ ADXS31-142 has a tropism for the liver. Transient asymptomatic elevations of ALT and alkaline phosphatase were observed after dosing with ADXS11-001 in the Phase 1 trial without prophylactic medication administration. For that reason, subjects with significant liver disease are excluded, and particular attention is to be paid to hepatic abnormalities.

The dose of ADXS31-142 will not be modified (e.g., reduced or increased) unless if it is determined that the toxicities are clearly attributed to ADXS31-142 or the combination, the treatment modification guidelines for drug-related AEs in [Table 9](#) shown below are to be followed.

Table 9 Treatment Delay/Discontinuation Guidelines for Drug-Related Adverse Events-ADXS31-142

Toxicity	Grade	Hold treatment	Timing for restarting treatment	Discontinue treatment
Hematologic	1-3	No	N/A	N/A
	4	Yes	Toxicity resolves to ≤Grade 1 or baseline	Toxicity does not resolve to ≤Grade 1 or baseline within 12 weeks
Non-hematologic, excluding cytokine release symptoms and DLTs	1	No	N/A	N/A
	2-3	Yes	Toxicity resolves to ≤Grade 1	Toxicity not resolved to ≤Grade 1 within 12 weeks of last infusion ^a
	4	N/A	Permanently discontinue treatment	Permanently discontinue treatment

^a With Investigator and Sponsor agreement, subjects with a non-heme AE (e.g., alopecia, neuropathy) still at grade 2 after 12 weeks, may continue treatment if only asymptomatic and controlled.

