5.2.2 Timing of Dose Administration

Trial treatment should be administered on Day 1 of Week 1, 4 and 7 (for ADXS31-142) or Q3W (for pembrolizumab [MK-3475]) in each 12-week cycle after all procedures/assessments have been completed as detailed on the Trial Flow Chart ([Section 6](#)). Trial treatment may be administered up to 7 days before or after the scheduled Day 1 of each cycle due to administrative reasons.

[figure not shown]
Trial treatments will be administered as a 30 minute IV infusion for pembrolizumab (MK-3475) and ██████████ (treatment cycle intervals may be increased due to toxicity as described in [Section 5.2.1.2](#)). Sites should make every effort to target required infusion timing. However, given the variability of infusion pumps from site to site, a window of ██████████ is permitted.

Patients will receive either oral 80 mg trimethoprim/400 mg sulfamethoxazole once daily for 7 days or 160 mg trimethoprim / 800 mg sulfamethoxazole (DS) three times over the course of the 7 days. Subjects with known allergy to sulfa drugs may receive ampicillin 500 mg four times daily for 7 days beginning on Day 4 (approximately 72 hours) after each study treatment infusion.

During combination dosing in Part B, there should be approximately [REDACTED] between the end of the first infusion and the start of the second infusion. The pembrolizumab (MK-3475) infusion will be administered first, followed by the ADXS31-142 required prophylactic regimen at least [REDACTED] prior to the ADXS31-142 infusion.

The Pharmacy Manual contains specific instructions for ADXS31-142 dose preparation and administration, and pembrolizumab (MK-3475) reconstitution, preparation of the infusion fluid, and administration.

5.2.3 *Administration of ADXS31-142*

5.2.4 *Pretreatment Prophylaxis Regimen*

Mild to moderate flu-like symptoms and cytokine release symptoms (e.g., constitutional symptoms such as fever, chills, rigors, fatigue, headache, nausea, vomiting, tachycardia, shortness of breath, hypotension, and rash) are commonly seen and typically occur 2-4 hours after immunotherapy and often resolve within 12-24 hours. Prophylactic medications are intended to reduce the inflammatory response. Prior to administering any prophylactic medications (on Day 1 of Weeks 1, 4, and 7 of each 12-week cycle), place a [REDACTED]

Subjects should receive the following pretreatment prophylaxis regimen through a temporary IV:

- IV Fluid Hydration:

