7.1.3.1 Laboratory Safety Evaluations (Hematology and Chemistry)

Laboratory tests for hematology, chemistry, and others are specified in [Table 15](#). The total amount of blood to be drawn over the course of the trial (from pre-trial to post-trial visits), including approximate blood by visit and by sample type per subject can be found in the Procedures Manual.

Table 15 Laboratory Tests

Hematology	Chemistry	Other
Hematocrit	Albumin	PT (INR) (screening only)
Hemoglobin	Alkaline phosphatase	aPTT (screening only)
Platelet count	Alanine aminotransferase (ALT)	Total triiodothyronine (T3)
WBC (total and differential)	Aspartate aminotransferase (AST)	Free thyroxine (T4)
Red Blood Cell Count	Lactate dehydrogenase (LDH)	Thyroid stimulating hormone (TSH)
Absolute Neutrophil Count	Carbon Dioxide (CO ₂ or bicarbonate)	
	Calcium	Serum creatinine OR creatinine clearance
	Chloride	Blood for correlative studies
	Creatinine	
	Glucose	
	Potassium	
	Sodium	
	Total Bilirubin	
	Direct Bilirubin (If total bilirubin is above the upper limit of normal)	

Hematology	Chemistry	Other
	Total protein	
	Blood Urea Nitrogen	
	Erythrocyte Sedimentation Rate*	
	C-Reactive Protein*	

Laboratory tests should be performed within 3 days prior to dosing. Results must be reviewed by the Investigator or qualified designee and found to be acceptable per Inclusion Criteria (Refer to [Table 3](#)) prior to each dose of trial treatment.

* *Lm* Surveillance Monitoring will include routine monitoring of CBC, CMP (including CRP, ESR) and blood cultures. Following completion of study treatment or at the time of study discontinuation, if earlier, testing will be performed on all subjects who have received at least one dose of ADXS31-142. It will occur every 3 months (+ 2 weeks) for 3 years beginning 3 months after the last dose of study treatment. CRP, ESR, and blood cultures are only collected during the *Lm* Surveillance Monitoring period, and not during the main part of the study. Lactate dehydrogenase (LDH) is only collected during the main part of the study, and is not collected during the *Lm* Surveillance Monitoring period (it is not part of the standard CMP).

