Adverse Event Monitoring - the Investigator or qualified designee will assess each subject to evaluate for potential new or worsening AEs as specified in the Schedule of Events and more frequently if clinically indicated. Adverse events will be graded and recorded throughout the study and follow-up according to CTCAE v 4.03. Toxicities will be characterized in terms regarding seriousness, causality, toxicity grading, and action taken with regard to trial treatment.

Physical Examination - evaluation by body system.

Vital Signs - blood pressure, pulse rate, respiratory rate, and temperature will be checked and recorded prior to administration of ADXS31-142 and every [REDACTED] for the first [REDACTED] following the completion of the ADXS31-142 infusion. For combination treatment, vital signs will be checked prior to pembrolizumab (MK-3475) administration, prior to the ADXS31-142 infusion and every [REDACTED] for the first [REDACTED] following the completion of the ADXS31-142 infusion. Weight will be collected once at every visit.

ECOG Performance Status - ECOG should be assessed prior to administration of study treatment.

Laboratory Tests - must be performed no more than 3 days prior to dosing. Screening labs can be used for Cycle 1 Day 1 labs, if performed within 3 days of dosing.

- **Hematology Profile** - a complete blood count with differential, and platelet count.
- **Chemistry Profile** - glucose, total protein, albumin, blood urea nitrogen, ESR, CRP, creatinine, AST, ALT, alkaline phosphatase, total bilirubin, phosphorus, sodium, potassium, bicarbonate, chloride, and calcium; thyroid function tests (TSH, T3, T4) during combination therapy only.
- **Urinalysis** - Routine dipstick measurements will be conducted as specified in the Study Flow Chart in [Section 6](#)

PO Antibiotics with Instructions - **(1) During Study Treatment Phase** - All subjects will receive a 7-day course of oral antibiotic therapy starting approximately 72 hours (Day 4) after administration of ADXS31-142. Antibiotic therapy should consist of either 160 mg trimethoprim/800 mg sulfamethoxazole (DS) tablet administered three times during the 7 consecutive days or 80 mg trimethoprim/400 mg sulfamethoxazole administered daily for 7 consecutive days or for subjects with sulfa allergy ampicillin 500 mg four times daily for 7 consecutive days may be administered.

Correlative studies: Blood will be collected as indicated below for immunology studies.

- [REDACTED]

- [REDACTED]

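### Section 7.1.3.1 requires Table 3 values before every dose, Table 9 says not to hold ADXS31-142 for hematologic Grade 1–3 toxicity, and nothing ranks the two rules

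*Combined protocol and SAP*

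**What the plan says.** Two parts of the protocol govern whether ADXS31-142 is given when a blood count is low.

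- **Pre-dose check.** The text under Table 15 in Section 7.1.3.1 says "Results must be reviewed by the Investigator or qualified designee and found to be acceptable per Inclusion Criteria". It points to Table 3 and covers each dose of trial treatment, not only the first. Table 3 (Section 5.1.2) requires hemoglobin of at least 9 g/dL, neutrophils of at least 1000/mcL, platelets of at least 75,000/mcL and lymphocytes of at least 500/mcL.
- **Dose-modification table.** Section 5.2.1.2.2 applies when "toxicities are clearly attributed to ADXS31-142 or the combination", and then directs that Table 9 be followed. That table is titled "Treatment Delay/Discontinuation Guidelines for Drug-Related Adverse Events-ADXS31-142". Its hematologic row answers No under the hold column for Grades 1 to 3 and Yes only for Grade 4.

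The same section lists, among the less likely adverse events, "changes in blood chemistry, changes in blood counts, and short term changes in liver function".

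**The concern.** A site that turns to the dose-modification section finds an unqualified No for hematologic Grades 1 to 3. A site that works from the laboratory section finds a mandatory threshold before every infusion. The two can give opposite instructions for the same patient on the same day.

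The stake is first a safety one. ADXS31-142 is a live attenuated *Listeria* product, and the Table 3 limits are the only numeric hematologic floor the protocol sets for dosing. If Table 9 prevails, a low hemoglobin firmly blamed on the drug is dosed through, while the same value from another cause is held. That ordering is hard to defend. The second stake is consistency: sites could handle identical values differently.

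**Working it through.** No figure in the plan needs reproducing. The check sets the rules side by side for one case.

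**Step 1: the test case.** Take a hemoglobin just under 9 g/dL after the first dose, clearly attributed to ADXS31-142 or the combination, with no life-threatening consequences. It fails Table 3. Table 16 reserves Grade 4 for life-threatening consequences needing urgent intervention, so a value graded as an adverse event here falls in Grades 1 to 3. I rely on hemoglobin alone. The CTCAE v4.03 cut-offs for the other counts are cited in Section 11.2 but not printed, so I do not say which neutrophil, platelet or lymphocyte values fall in the gap.

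**Step 2: the two answers.**

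| Rule | Trigger met? | Instruction for ADXS31-142 |
|---|---|---|
| Section 7.1.3.1 with Table 3 | Yes: applies before every dose | Not acceptable, so no dose |
| Section 5.2.1.2.2 with Table 9 | Yes: clearly attributed, Grade 1–3 | Do not hold |

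**Step 3: does any text rank them?**

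- Section 5.2.2 has dosing follow "after all procedures/assessments have been completed as detailed on the Trial Flow Chart". It requires the assessments and sets no acceptability rule.
- Section 7.1.5.2 says laboratory tests "must be performed no more than 3 days prior to dosing". That is a time window only.
- The opening of Section 7.1.5 refers back to Section 7.1 for procedural detail. This supports the Table 3 check applying at dosing visits but says nothing about Table 9.
- Section 5.2.1.1.1 sends DLT handling to Tables 8 and 9 and does not mention the check. It requires discontinuation after a DLT at Dose Level -1, which settles that subset without ranking the rules.
- Section 7.1.3.1 makes no exception for attributed toxicity, and Section 5.2.1.2.2 does not mention the check.

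**Step 4: how far it reaches.**

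- Attribution: Table 9 needs clear attribution. DLT scoring uses a wider net, "possibly, probably or definitely related to study treatment administration". A count that is only possibly related may not engage Table 9, and then Section 7.1.3.1 governs alone.
- Pembrolizumab: Table 8 has no row telling sites not to hold for low counts, so Section 7.1.3.1 has no competitor there.
- Part A: Section 5.2.1.1.2 says it is completed. Only Part B is affected.

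**Step 5: does the choice change DLT status?** Dose 2 of both drugs is due on Day 1 of Week 4, which is 3 × 7 + 1 = Day 22. A delay of more than 2 weeks runs past 22 + 14 = Day 36. General criterion 1 is "Prolonged delay (>2 weeks) in initiating the second dose due to treatment-related toxicity" and names no drug. General criterion 2 covers a missed second dose of either drug because of adverse events.

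- Site follows Section 7.1.3.1: both drugs are held. Past Day 36, criterion 1 is met. If dose 2 is missed, criterion 2 is met.
- Site follows Table 9 for ADXS31-142: pembrolizumab is still barred. If it slips past Day 36, criterion 1 can be read as met. If it is missed, criterion 2 is met.

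The two routes therefore probably give the same DLT status. I say probably because the observation window closes one week after ADXS31-142 dose 2. If that dose is on time, the window closes on 22 + 7 = Day 29, and the text does not say how a pembrolizumab delay completed after that is scored.

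**The case against.** The strongest reply is that the rules are additive. Section 7.1.3.1 states a necessary condition in mandatory terms. Table 9 calls itself guidelines, and its No can mean only that the grade does not by itself require a hold. The back-reference in Section 7.1.5 fits that reading. It is a sensible reading, and the fix below adopts it. But it remains the reader's inference. Section 5.2.1.2.2 makes Table 9 directive, and the table states exceptions where it wants them: its non-hematologic row carves out cytokine release symptoms and DLTs, while the hematologic row carves out nothing.

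It can also be said that the case is rare. That stands. Section 4.2.2.1 describes adverse events in this class as nearly all low grade, blood-count changes are listed as less likely, and clear attribution is required.

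A reader might infer something stronger: that extra delay-based DLTs would tip the Part B 3+3 rule toward de-escalation. The documents do not support this, for four reasons.

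- Step 5 shows that a long hold probably counts as a DLT whichever rule a site follows.
- A long hold is not the expected course. Table 3 footnote a restricts transfusion only in the 2 weeks before treatment initiation and does not say that it carries over to later doses. Section 5.5.1 allows treatment the investigator finds necessary, and Section 5.5.2 does not list transfusion as prohibited.
- No rate of such events is given, so any shift in de-escalation probability would rest on an invented input.
- Section 5.2.1.1 has the sponsor and investigators confer before any de-escalation, which may catch a disputed case. That discussion does not, however, tell a site whether to infuse that day.

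**Conclusion.** The concern holds as a conflict between two dosing rules, wrong as written and minor in severity. A clearly attributed, non-Grade-4 value below Table 3 is barred by Section 7.1.3.1 and not held by Table 9, with no stated precedence. The consequence is inconsistent and possibly less safe ADXS31-142 dosing in Part B.

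The size cannot be put in numbers, because the documents do not say how often such values occur. The conclusion rests on the Table 16 description of Grade 4 and is shown for hemoglobin only. It does not extend to pembrolizumab or to Part A, and it is not a finding that the recommended Phase 2 dose would change.

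**What to change.** Change the Table 9 hold cell for hematologic Grades 1 to 3 to read: *No, provided pre-dose labs meet Table 3 (Section 7.1.3.1); otherwise hold until they do.* Repeat the condition in one sentence under the laboratory tests in Section 7.1.5.2. Table 8 needs no change.

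This keeps a check the protocol already states as mandatory. It takes one table cell and one sentence, with no added visits, tests or subjects. The downside is a few more held ADXS31-142 doses.

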7.1.4 Other Procedures

7.1.4.1 Withdrawal/Discontinuation

When a subject discontinues/withdraws prior to trial completion, all applicable activities scheduled for the final trial visit should be performed at the time of discontinuation. Any AEs which are present at the time of discontinuation/withdrawal should be followed in accordance with the safety requirements outlined in [Section 7.2](#). Subjects who a) attain a CR or b) complete 24 months of treatment may discontinue treatment. After discontinuing treatment following assessment of CR, these subjects should return to the site for a Safety Follow-up Visit (described in [Section 7.1.5.3](#)) and then proceed to the Follow-Up Period of the study (described in [Section 7.1.5.3](#)).

7.1.5 Visit Requirements

Visit requirements are outlined in [Section 6](#). Specific procedure-related details are provided above in [Section 7.1](#).

7.1.5.1 Screening Period

Screening period – this 28-day period will start when the first screening evaluation is performed. This does not include signing of Informed Consent or wash-out periods.

Informed Consent - prior to conducting screening evaluations each subject must sign a copy of the most current Institutional Review Board/Independent Ethics Committee

(IRB/IEC) approved informed consent document. A copy of the signed document will be maintained with the subject's records.

Screening evaluations - will be performed after Informed Consent is signed and within 28 days prior to first dose of study treatment.

Laboratory Tests - must be performed no more than 28 days prior to first dose but may be used as Cycle 1 Day 1 safety labs if done within 3 days of first dose.

Inclusion/Exclusion Criteria - all inclusion and exclusion criteria will be reviewed by the Investigator or qualified designee to ensure that the subject qualifies for the trial.

Medical History/Prior and Concomitant Medications - past or current medical conditions, past surgeries, current medications, medications taken within 28 days of study entry, histological confirmation of cancer, tumor staging (refer to the most current American Joint Committee on Cancer Staging Manual, the 5th edition or higher), and prior cancer therapies and best response(s), if applicable.

7.1.5.2 *Treatment Period*

Subjects will be treated for approximately 2 years. Subjects should arrive at the study center early on the days of their scheduled treatment in order to be evaluated, take study prophylactic medication at least 30 minutes prior to ADXS31-142 infusion, and have laboratory specimens collected before treatment commences. For Cycle 1 Day 1 pre-treatment laboratory specimens do not need to be collected if screening labs were collected within 3 days of first dose.

During the time the subjects are at the study site for ADXS31-142 or combination treatment (on Day 1 of Weeks 1, 4, and 7 of each 12-week cycle), all IV study medications must be administered through a temporary IV, which will be removed prior to discharge. Subjects will remain at the study center for a minimum of 4 hours after study treatment for safety observation, and if necessary, treatment of side effects. Additional doses of NSAIDs and antiemetics post ADXS31-142 infusion may be administered per label or package insert, as needed.

Adverse Event Monitoring - the Investigator or qualified designee will assess each subject to evaluate for potential new or worsening AEs as specified in the Schedule of Events and more frequently if clinically indicated. Adverse events will be graded and recorded throughout the study and follow-up according to CTCAE v 4.03. Toxicities will be characterized in terms regarding seriousness, causality, toxicity grading, and action taken with regard to trial treatment.

Physical Examination - evaluation by body system.

Vital Signs - blood pressure, pulse rate, respiratory rate, and temperature will be checked and recorded prior to administration of ADXS31-142 and every [REDACTED] for the first [REDACTED] following the completion of the ADXS31-142 infusion. For combination treatment, vital signs will be checked prior to pembrolizumab (MK-3475) administration, prior to the ADXS31-142 infusion and every [REDACTED] for the first [REDACTED] following the completion of the ADXS31-142 infusion. Weight will be collected once at every visit.

ECOG Performance Status - ECOG should be assessed prior to administration of study treatment.

Laboratory Tests - must be performed no more than 3 days prior to dosing. Screening labs can be used for Cycle 1 Day 1 labs, if performed within 3 days of dosing.

- **Hematology Profile** - a complete blood count with differential, and platelet count.
- **Chemistry Profile** - glucose, total protein, albumin, blood urea nitrogen, ESR, CRP, creatinine, AST, ALT, alkaline phosphatase, total bilirubin, phosphorus, sodium, potassium, bicarbonate, chloride, and calcium; thyroid function tests (TSH, T3, T4) during combination therapy only.
- **Urinalysis** - Routine dipstick measurements will be conducted as specified in the Study Flow Chart in [Section 6](#)

PO Antibiotics with Instructions - **(1) During Study Treatment Phase** - All subjects will receive a 7-day course of oral antibiotic therapy starting approximately 72 hours (Day 4) after administration of ADXS31-142. Antibiotic therapy should consist of either 160 mg trimethoprim/800 mg sulfamethoxazole (DS) tablet administered three times during the 7 consecutive days or 80 mg trimethoprim/400 mg sulfamethoxazole administered daily for 7 consecutive days or for subjects with sulfa allergy ampicillin 500 mg four times daily for 7 consecutive days may be administered.

Correlative studies: Blood will be collected as indicated below for immunology studies.

- [REDACTED]

- [REDACTED]

Tumor Imaging/Disease Assessment - CT scan, MRI or bone scan for determination of unidimensional measurements and disease response. Baseline tumor imaging/disease assessment must be performed within 28 days prior to the first dose of ADXS31-142 and at Week 10 (\pm 1 week) for the first cycle and then every 12 weeks (\pm 1 week). Imaging areas will include the chest, abdomen, pelvis, and other areas as indicated by clinical presentation.

